Cover Page

ID: 5160230

Benefit of Adding Stretching to Standard
Intervention for Patients with
Nonspecific Mechanical Neck Pain

NCT03194490

Date: October 09, 2019

Methods

Participants

Forty-three participants who had at least two weeks of non-specific mechanical neck pain were randomly assigned to either the combined intervention (passive cervical mobilization, active range of motion exercises, and stretching techniques) ($n_1=20$) or standard intervention group (passive cervical mobilization and active range of motion exercises) ($n_2=23$). At two-weeks follow-up, 2 participants dropped out of the study due to health conditions, and at 8 weeks, 3 participants withdrew. (Refer to Figure 1) Thus, 38 participants with a mean age 31.0 ± 8.3 years, height 1.6 ± 0.1 m, mass 72.8 ± 17.5 kg, and body mass index 26.9 ± 6.7 kg/m² completed this study. All participants read and signed a consent form that was approved by the institutional review board at Loma Linda University. This study was registered in ClinicalTrials.gov with Protocol #5160230. The participants met the following inclusion criteria: between 18 and 60 years of age, had non-specific neck pain for at least 2 weeks, and pain intensity of more than 2 points on a numeric pain rating scale (NPRS) in the past week. Participants were excluded from the study if they had one or more of the following conditions: specific diagnosis of the cervical spine, such as spinal stenosis, disc prolapse, previous surgery in the neck and shoulder areas, shoulder pathology (bursitis, tendonitis, adhesive capsulitis), history of severe trauma, ligamentous instability, hypermobility syndrome, migraine (frequency more than twice per month), spasmodic torticollis, radiculopathy due to peripheral nerve entrapment, fibromyalgia, severe psychiatric illness, inflammatory rheumatic diseases, pregnancy or other on-going therapies.

The identification of the study's excluding criteria was conducted through clinical examination, medical history and self-reported questionnaires ⁶. Participants were randomly assigned to either the combined intervention group or the standard intervention group using a random number table. Demographic and general characteristics of the participants are presented in **Table 1**.

Instrumentation

Cervical ROM

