The study was conducted over 8 weeks. Participants were randomly allocated into two groups: *combined intervention* (passive cervical mobilization, active range of motion exercises, and stretching techniques) ($n_1=18$) and *standard intervention groups* ($n_2=20$). The randomization was performed by a person who was blind to the patient's allocation. Participants in the *combined intervention group* received 30 minutes of passive manual therapy consists of (i) cervical mobilization and (ii) active cervical range of motion exercises to be performed at home 3-4 times daily, (iii) stretching techniques for 2 sessions per week for 4 weeks (iv) a self-administered stretching exercises to be performed at home 5 times a week. Participants in *standard intervention group* received 15 minutes of manual therapy consists of (i) cervical mobilization and (ii) active range of motion exercises to be performed at home 3-4 times daily.

Cervical Mobilization techniques were used in the study and consisted of low-velocity non-thrust cervical joint mobilizations for unilateral symptoms: postero-anterior unilateral vertebral pressure, traction, and transfer vertebral pressure. For bilateral symptoms, the following joint mobilization were applied: postero-anterior central vertebral pressure, postero-anterior unilateral vertebral pressure (2 sides), longitudinal movement, traction and rotation. These techniques have been described previously by Anandacoomarasamy, Barnsley³¹. Both groups received 10 minutes of cervical mobilization for 2 sessions per week for 4 weeks.

Active Cervical Range of Motion Exercises (ACROM) were performed 10 repetitions 3–4 times daily. The ACROM exercise consisted of the subject placing four fingers over the manubrium bone and placing chin on the fingers. The subject was then instructed to rotate to one side as far as possible and return to neutral and then actively rotate to the other side³². Both groups performed ACROM exercises. Subjects were advised to maintain their usual activity within the limits of pain.

Stretching techniques were performed in the combined intervention group for 30 seconds for each muscle and repeated 3 times twice a week to the following muscles: anterior, middle and posterior scalene, upper fibers of trapezius, pectoralis minor muscles and interspinous muscles as described by Ylinen, Chaitow, Nurmenniemi, Hill ³³.

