The cervical mobilization and stretching exercise techniques were performed by a licensed physical therapist who has 6 years of experience in manual physical therapy.

Self-administered stretching exercises were performed by participants in the combined intervention group to the following muscles: the extensor muscles, the upper part of the trapezius, and the posterior scalene ⁶. Each movement was held for 30 seconds and repeated 3 times. Lastly, the participant was instructed to perform a neck straightening exercise by retracting the neck (Chin tuck) 5 times for 3-5 seconds. Subjects in the combined intervention group were provided with written instruction of the stretching exercises and directed to perform stretching exercise 5 times a week, each exercise session takes about 10 minutes. Patients were also instructed to keep a stretching diary to track their stretch exercise frequency.

Data collection:

Data was collected at baseline, one week after intervention, and week 4. The final data collection date was set at week 8 as a follow up to determine whether the participant was able to maintain gains at one month following the interventions.

Statistical Analyses

A sample size of 50 participants was estimated using a moderate effect size of 0.25, level of significance 0.05, and power of 0.80. Data was summarized using mean and standard deviation ¹ for quantitative variables and counts (%) for qualitative variables. The normality of continuous variables was examined using Shapiro Wilk's test. The distribution of the participants' characteristics by study group were evaluated using chi-square for qualitative variables and independent t- test for quantitative variables. Mixed factorial analysis of variance (ANOVA) was used to examine changes in cervical ROM variables, pressure pain threshold, NPRS, GROC, and NDI scores by study group over time. Post hoc comparisons using Bonferroni test and effect size were computed to identify significant differences over time. We compared percent change (4 weeks vs. baseline) for all outcome variables between the two study groups using independent t- test and Mann- Whitney test. To examine whether there were any changes in the outcome variables at 4 weeks follow up paired t- test was used. The level of significance was set at $p \leq 0.05$. Statistical analysis was performed using IBM SPSS Software version 24 for Windows (Chicago, IL, USA).

Results

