There was a significant difference in mean NPRS over time ($F_{2,72}=47.8$, $p<0.001$, $\eta^2=0.60$), however, there was no significant group by time interaction ($F_{2,72}=1.5$, $p=0.23$), and the improvement did not differ significantly by study group ($F_{1,36}=1.4$, $p=0.24$). Bonferroni post hoc comparison revealed that the difference was significant between baseline and one week later (4.7 ± 0.3 vs. 3.3 ± 0.3 , $p<0.001$), baseline and 4 weeks later (4.7 ± 0.3 vs. 1.7 ± 0.3 , $p<0.001$), and between one week later and 4 weeks (3.3 ± 0.3 vs. 1.7 ± 0.3 , $p<0.001$).

Change in GROG

For GROG, there was a significant difference over time ($F_{1,36}=42.9$, $p<0.001$, $\eta^2=0.54$), however, there was no significant group by time interaction ($F_{1,36}=0.001$, $p=0.98$), and the improvement was not significantly different by study group ($F_{1,36}=0.7$, $p=0.40$). Bonferroni post hoc comparison revealed that the difference was significant between one week later and 4 weeks (2.4 ± 0.3 vs. 4.7 ± 0.4 , $p<0.001$). (Refer to **Table 3**).

Change in NDI

There was a significant difference in mean NDI over time ($F_{2,72}=38.2$, $p<0.001$, $\eta^2=0.52$), however, there was no significant group by time interaction ($F_{2,72}=2.8$, $p=0.07$), and the improvement over time did not differ by study group ($F_{1,36}=0.0$, $p=0.98$). Bonferroni post hoc comparison revealed that the difference was significant between baseline and one week later (11.2 ± 0.8 vs. 7.6 ± 0.7 , $p<0.001$), baseline and 4 weeks later (11.2 ± 0.8 vs. 4.5 ± 0.8 , $p<0.001$), and between one week later and 4 weeks (7.6 ± 0.7 vs. 4.5 ± 0.8 , $p<0.001$). After 4 weeks follow up, there were no significant changes in all the outcome variables by study group. (Refer to **Table 4**)

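### Week 8 was set to check whether gains last, but the only method described is a paired test of change, which cannot show maintenance, and no between-arm method for week 8 is described

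*Combined protocol and SAP*

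**What the plan says.** Data collection lists baseline, one week, week 4 and week 8. The stated purpose of the last visit is "to determine whether the participant was able to maintain gains at one month following the interventions".

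Three relevant methods are named under Statistical Analyses. A mixed factorial ANOVA compares the arms over time. Percent change is compared between arms, but only for 4 weeks against baseline. For the follow-up period the text says: "To examine whether there were any changes in the outcome variables at 4 weeks follow up paired t- test was used".

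The result is one sentence at the end of Change in NDI: "After 4 weeks follow up, there were no significant changes in all the outcome variables by study group". It points to Table 4, which is not in the supplied text. The text gives no maintenance margin, no confidence interval and no equivalence or non-inferiority test for week 8.

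**The concern.** Maintenance is a claim that little or nothing was lost. The null hypothesis of a paired t-test is that nothing changed. Failing to reject it is compatible with full maintenance and, if the estimate is imprecise, with a material loss. The planned test therefore cannot answer the question for which the visit was scheduled.

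The trial asks whether adding stretching helps, and it reports group-by-time interactions up to week 4 for extension and both lateral flexions. Whether that difference persists a month later is a between-arm question. A paired test compares visits within people, not arms, and the analyses described as comparing arms do not reach week 8.

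**Working it through.** **1. Which visits the between-arm analyses cover.** For a mixed ANOVA with k visits, 38 participants and two arms, the time and interaction degrees of freedom are (k−1) and (38−2)(k−1).
- ROM, pressure pain threshold, NPRS and NDI are reported with 2 and 72: k−1 = 2 and 36×2 = 72, so k = 3 (baseline, week 1, week 4).
- GROC is reported with 1 and 36, so k = 2 (week 1, week 4).
- Percent change is defined as 4 weeks against baseline.

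Week 8 is in none of them. Because baseline to week 4 changes are reported as significant, the 4 weeks follow-up in the paired-test sentence is read as week 4 to week 8.

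**2. SD of a between-visit change.** The documents give none for week 4 to 8, so it is assumed similar to that of the earlier visits. There are two routes.

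*From the reported F for time.* MS(time) = 38 × Σ(mean − grand mean)²/2; MSE = MS/F; SD of change = √(2×MSE).
- Extension: means 70.2, 74.3, 76.6; sum of squares 21.02; MS 399.4; MSE 399.4/6.8 = 58.7; SD 10.8.
- Right lateral flexion: 40.8, 43.8, 46.8; MS 342; MSE 342/13.8 = 24.8; SD 7.0.
- NDI: 11.2, 7.6, 4.5; MS 427.2; MSE 427.2/38.2 = 11.2; SD 4.7.
- NPRS: 4.7, 3.3, 1.7; MS 85.6; MSE 85.6/47.8 = 1.79; SD 1.9.

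Reading the ± values as SEs, these imply between-visit correlations (1 − MSE/variance) of 0.48 to 0.67, which is plausible. Read as SDs, they would give an impossible correlation for extension: the mean variance would be 4.7 against an MSE of 58.7.

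*From the week 1 to week 4 comparison, extension.* The difference is 76.6 − 74.3 = 2.3, with Bonferroni p = 0.15. If p is three times the raw value on 36 df, raw p = 0.05, t = 2.03, SE = 2.3/2.03 = 1.13, and SD of change = 1.13×√38 = 7.0.

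**3. Precision of a paired comparison (two-sided 0.05).** Half-width = t(0.975, n−1) × SD/√n. At n=18 this is 2.11 × SD/4.243 = 0.497 SD. The loss detectable with 80% power (noncentral t) is 0.70 SD at n=18, 0.66 SD at n=20 and 0.47 SD at n=38.

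| n=18 | SD of change | Half-width | 80% detectable loss | Pooled gain | Power, loss of half the gain |
|---|---|---|---|---|---|
| Extension (degrees) | 7.0 to 10.8 | 3.5 to 5.4 | 4.9 to 7.6 | 6.4 | 45% to 22% |
| Right lateral flexion (degrees) | 7.0 | 3.5 | 4.9 | 6.0 | 40% |
| NDI (points) | 4.7 | 2.3 | 3.3 | 6.7 | 81% |
| NPRS (points) | 1.9 | 0.9 | 1.3 | 3.0 | 89% |

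Pooled at n=38, extension has 78% to 43% power for the same loss. The right lateral flexion row uses the F route only. Its week 1 to week 4 comparison (3.0 degrees, p = 0.001), treated as in step 2, gives an SD of about 4.7 and power of about 73%.

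**4. Against each arm's own gain in extension.** Changes in ROM gives 18.9% (combined) and 3.0% (standard). Applied to the pooled baseline of 70.2, because arm baselines are not shown, these are about 13.3 and 2.1 degrees. The n=18 half-width is then 26% to 41% of the combined arm's gain (3.5/13.3 to 5.4/13.3). The n=20 half-width, 3.3 to 5.1 degrees, exceeds the standard arm's whole gain.

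**The case against.** Five stronger readings are tempting, and the documents do not support them.

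- *The arms were tested separately.* The methods sentence names a paired t-test without saying per arm or pooled. Per-arm testing is an inference from the phrase about study group in the result. The point about maintenance is the same either way.
- *There is no between-arm result at week 8.* Elsewhere in the results, the phrase by study group accompanies between-arm F tests for NPRS, GROC and NDI. The follow-up sentence may be such a statement, and Table 4 may hold the estimates. What can be said is that the supplied text describes no between-arm method and gives no estimate or interval for week 8.
- *The authors conclude that gains were maintained.* They report no significant changes and stop there. A reader may take this as maintenance because that was the purpose of the visit, but the text does not say it.
- *A large loss would be missed on any outcome.* For NDI and NPRS, loss of half the pooled gain would probably be detected.
- *The detectable loss in extension exceeds the whole gain.* This holds only at the upper SD and against the pooled gain. At the lower SD it is 4.9 degrees, below 6.4, and the combined arm's own gain is roughly twice the pooled one.

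It is also fair to object that the F-based inputs are fragile. For extension, F = 6.8 on 2 and 72 df gives a partial eta-squared of 13.6/85.6 = 0.16, while the text reports 0.20. That is a reason to give ranges. It does not affect the logical point, which needs no power calculation.

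**Conclusion.** The point holds in limited form. The method described for week 8 tests for change and cannot establish maintenance, and the between-arm analyses described stop at week 4. Neither statement depends on power or on how the paired tests were grouped; the second is subject to what Table 4 contains.

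The size of the imprecision varies by outcome. For extension at n=18 the interval is about ±3.5 to ±5.4 degrees against a pooled gain of 6.4, so an arm could lose much of a gain of that size without a significant test. For right lateral flexion, power against loss of half the pooled gain is about 40% on the F-based SD, and higher on the alternative one. For NDI and NPRS the concern about power is weak.

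These figures assume that the ± values are SEs, that the week 4 to 8 change varies about as much as earlier changes, and that tests are two-sided at 0.05. The week 4 comparison is unaffected.

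**What to change.** Include week 8 in the repeated-measures model with baseline, week 1 and week 4; for GROC, which has no baseline, with week 1 and week 4. Report, with 95% CIs:
- the between-arm difference in change from baseline at week 8 (for GROC, the between-arm difference at week 8);
- each arm's change from week 4 to week 8.

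Base any statement on maintenance on where that interval lies relative to the arm's own baseline to week 4 gain, not on p>0.05. State whether the existing paired tests were per arm or pooled, and, if Table 4 already holds a between-arm comparison, describe its method in Statistical Analyses.

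The cost is a re-analysis of data already collected. The downside is that conclusions on maintenance become more cautious, chiefly for range of motion.

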Thirty-eight (38) subjects with a mean \pm SD age 30.9 ± 8.1 years and body mass index (BMI) 26.8 ± 6.7 kg/m² participated in the study. Sixty- five percent of the participants were females (n=

26). There was no significant difference between the two study groups in terms of age, Body Mass Index (BMI), cervical ROM and pressure pain threshold at baseline. Demographic and general characteristics are presented in **Table 1**.

Changes in ROM

Results of the mixed factorial ANOVA for ROM is displayed in **Table 2**. There was a significant difference in mean ROM during extension over time ($F_{2,72}=6.8$, $p=0.002$, $\eta^2=0.20$), and a significant group by time interaction ($F_{2,72}=3.6$, $p=0.02$). Bonferroni post hoc comparison revealed that the difference was significant between baseline and one week later (70.2 ± 2.1 vs. 74.3 ± 2.4 , $p=0.04$), baseline and 4 weeks later (70.2 ± 2.1 vs. 76.6 ± 2.0 , $p=0.001$), however, there was no significant difference between one week later and 4 weeks ($p=0.15$). In addition, the % improvement from baseline to 4 weeks later was significantly different between the combined intervention and standard intervention groups respectively (18.9% vs. 3.0% ; $t=2.4$, $p=0.02$). (Refer to **Table 2**)

Also, there was a significant difference in mean ROM during right lateral flexion over time ($F_{2,72}=13.8$, $p<0.001$, $\eta^2=0.30$), and a significant group by time interaction ($F_{2,72}=2.9$, $p=0.04$). Bonferroni post hoc comparison revealed that the difference was significant between baseline and one week later (40.8 ± 1.5 vs. 43.8 ± 1.3 , $p=0.03$), baseline and 4 weeks later (40.8 ± 1.5 vs. 46.8 ± 1.4 , $p<0.001$), and between one week later and 4 weeks (43.8 ± 1.3 vs. 46.8 ± 1.4 , $p=0.001$). In addition, the % improvement from baseline to 4 weeks later was significantly different between the combined intervention and groups respectively (23.2% vs. 10.8% ; $t=1.8$, $p=0.04$). (Refer to **Table 2**).

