There was a significant difference in mean ROM during left lateral flexion over time ($F_{2,72}=3.0$, $p=0.03$, $\eta^2=0.30$), and a significant group by time interaction ($F_{2,72}=3.0$, $p=0.03$). Bonferroni post hoc comparison revealed that the difference was significant between baseline and one week later (43.0 ± 1.1 vs. 46.3 ± 1.0 , $p=0.01$), baseline and 4 weeks later (43.0 ± 1.1 vs. 48.5 ± 1.3 , $p<0.001$), and between one week later and 4 weeks (46.3 ± 1.0 vs. 48.5 ± 1.3 , $p=0.01$). In addition, the percent improvement from baseline to 4 weeks later was significantly more for the combined intervention as compared to the standard intervention group (20.0% vs. 7.7% ; $t=2.1$, $p=0.02$).

For the other ROM directions, flexion, right rotation, and left rotation, both groups had a significant improvement in mean ROM over time ($p<0.05$), however, this improvement was not significantly different between the two groups. (Refer to **Table 2**).

Change in Pressure Pain Threshold (PPT)

There was a significant difference in mean right upper trapezius muscle pressure pain threshold over time ($F_{2,72}=4.3$, $p=0.02$, $\eta^2=0.11$), however, there was no significant group by time

interaction ($F_{2,72}=0.98$, $p=0.38$), and the change over time was not significantly different between the two groups ($F_{2,72}=0.02$, $p=0.90$). Bonferroni post hoc comparison revealed that the difference was significant between baseline and 4 weeks later (4.7 ± 0.3 vs. 5.5 ± 0.3 , $p=0.01$), and between one week later and 4 weeks (4.7 ± 0.3 vs. 5.5 ± 0.3 , $p=0.01$). For left pressure pain threshold, there was a significant difference over time ($F_{2,72}=8.4$, $p=0.001$, $\eta^2=0.20$), however, there was no significant group by time interaction ($F_{2,72}=0.48$, $p=0.59$), and the change over time was not significantly different between the two groups ($F_{2,72}=0.02$, $p=0.86$). Bonferroni post hoc comparison revealed that the difference was significant between baseline and 4 weeks later (4.5 ± 0.3 vs. 5.7 ± 0.4 , $p=0.005$), and between one week later and 4 weeks (4.5 ± 0.2 vs. 5.7 ± 0.4 , $p=0.001$). (Refer to **Table 3**).

Changes in NPRS

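### Five of the eight printed eta-squared values exceed what their own F and degrees of freedom give, led by left lateral flexion (0.30 printed, 0.08 implied), and every eta-squared in the text is for change over time pooled across arms

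*Combined protocol and SAP*

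**What the plan says.** Statistical Analyses plans a mixed factorial ANOVA by group and time, and says that post hoc Bonferroni tests and "effect size were computed to identify significant differences over time". The same section also plans a between-group comparison of percent change from baseline to 4 weeks.

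The Results then attach an eta-squared to each of eight time effects:

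- Changes in ROM: "mean ROM during extension over time ($F_{2,72}=6.8$, $p=0.002$, $\eta^2=0.20"; "mean ROM during right lateral flexion over time ($F_{2,72}=13.8$, $p<0.001$, $\eta^2=0.30"; "mean ROM during left lateral flexion over time ($F_{2,72}=3.0$, $p=0.03$, $\eta^2=0.30".
- Change in Pressure Pain Threshold, right side: "pressure pain threshold over time ($F_{2,72}=4.3$, $p=0.02$, $\eta^2=0.11".
- The same section, left side: "there was a significant difference over time ($F_{2,72}=8.4$, $p=0.001$, $\eta^2=0.20".
- Changes in NPRS: "mean NPRS over time ($F_{2,72}=47.8$, $p<0.001$, $\eta^2=0.60".
- GROC: F(1,36) = 42.9 with 0.54. NDI: F(2,72) = 38.2 with 0.52.

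Each group-by-time interaction is given an F and a p, but no eta-squared. For left lateral flexion the interaction is printed as F(2,72) = 3.0, p = 0.03, identical to the time effect.

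**The concern.** Eta-squared for a term in this design is fixed by the F and degrees of freedom printed beside it, so the two can be checked against each other. Several pairs do not agree, and every disagreement makes the effect look larger. Effect size is a planned statistic here, and these eight values are the only standardised effect sizes in the visible text. A later reader or meta-analyst may lift them directly.

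There is also a question of what they measure. The trial asks what stretching adds to standard treatment. In a two-arm repeated-measures design that is the group-by-time interaction. A time main effect is the improvement shared by both arms and says nothing about the added component.

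**Working it through.** **Inputs.** F, degrees of freedom and eta-squared as printed in the Results subsections listed above. The error degrees of freedom agree with 38 analysed participants in 2 groups at 3 occasions: (38 − 2) × (3 − 1) = 72. GROC, with two occasions, has 36.

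**Formula.** Partial eta-squared = df1×F / (df1×F + df2). Each F is printed to one decimal, so the range uses F ± 0.05.

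**Values that reproduce.**

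- Right PPT: 8.6/80.6 = 0.107 (printed 0.11).
- GROC: 42.9/78.9 = 0.544 (printed 0.54).
- NDI: 76.4/148.4 = 0.515, range 0.5145 to 0.5152. The printed 0.52 is reached only at the top of that range.

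**Values that do not.**

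| Time effect | F(2,72) | Calculation | Result (range) | Printed | Printed ÷ result |
|---|---|---|---|---|---|
| Left lateral flexion | 3.0 | 6.0/78.0 | 0.077 (0.076–0.078) | 0.30 | 3.9 |
| Extension | 6.8 | 13.6/85.6 | 0.159 (0.158–0.160) | 0.20 | 1.26 |
| Right lateral flexion | 13.8 | 27.6/99.6 | 0.277 (0.276–0.278) | 0.30 | 1.08 |
| Left PPT | 8.4 | 16.8/88.8 | 0.189 (0.188–0.190) | 0.20 | 1.06 |
| NPRS | 47.8 | 95.6/167.6 | 0.570 (0.570–0.571) | 0.60 | 1.05 |

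**Could another definition explain them?** Classical eta-squared cannot exceed partial eta-squared. A sphericity correction multiplies both degrees of freedom by the same factor and leaves partial eta-squared unchanged. Omega-squared and epsilon-squared are smaller still. No single variant tried reproduces all five.

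**Which item is wrong?** The F needed for a printed value E is E/(1 − E) × df2/df1.

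- *Left lateral flexion:* 0.30/0.70 × 36 = 15.4, against 3.0 printed. F(2,72) = 3.0 also gives p = 0.056, not the printed 0.03. With F and p repeated for the interaction, a copying error in the time F is the likeliest explanation. The post hoc p < 0.001 for baseline against 4 weeks also sits more easily with a large time F. Only the source output can settle it.
- *Extension:* 0.20/0.80 × 36 = 9.0, which gives an uncorrected p of 0.0003. F = 6.8 gives p = 0.0020, matching the printed 0.002. If the p is uncorrected, the F stands and 0.20 is the wrong item.
- *Left PPT:* uncorrected, F = 8.4 gives p = 0.0005 and F = 9.0 gives 0.0003, which would favour the printed F. But the interaction for this outcome is printed as F = 0.48, p = 0.59, and uncorrected that F gives 0.62. A sphericity correction with epsilon of 0.85 (assumed; the documents state none) gives 0.59. Under it F = 8.4 gives p = 0.0011 and F = 9.0 gives 0.0007, both printed as 0.001. The p cannot decide here.
- *Right lateral flexion and NPRS:* p is printed only as < 0.001, which does not discriminate.

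**Interaction effect sizes from the printed F.**

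| Outcome | Interaction F | Partial eta-squared, interaction | Printed, time |
|---|---|---|---|
| Extension | 3.6 | 7.2/79.2 = 0.09 | 0.20 |
| Right lateral flexion | 2.9 | 5.8/77.8 = 0.07 | 0.30 |
| Left lateral flexion (if its F stands) | 3.0 | 6.0/78.0 = 0.08 | 0.30 |
| NPRS | 1.5 | 3.0/75.0 = 0.04 | 0.60 |
| NDI | 2.8 | 5.6/77.6 = 0.07 | 0.52 |
| Right PPT | 0.98 | 1.96/73.96 = 0.03 | 0.11 |
| Left PPT | 0.48 | 0.96/72.96 = 0.01 | 0.20 |
| GROC, F(1,36) | 0.001 | 0.001/36.001 = 0.00 | 0.54 |

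**The case against.** Four of the five discrepancies are largely a matter of precision. The values 0.159, 0.277, 0.189 and 0.570 round to 0.2, 0.3, 0.2 and 0.6, and a trailing zero gives what is printed. The gaps are 0.01 to 0.04, and their common upward direction only reflects where these four values happen to fall. That stands, and it makes them minor. It does not make them correct: printed beside 0.11, 0.52 and 0.54, they claim two decimals. It also does not cover left lateral flexion, which would round to 0.1.

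On the second part, each eta-squared sits in a sentence about change over time, and the interaction follows with its own F and p. For PPT, NPRS, GROC and NDI the text says plainly that the interaction was not significant. A careful reader would not mistake one for the other. This too stands, so the missing interaction effect size is a gap in reporting rather than an arithmetic error.

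A reader might infer that the trial offers nothing on the size of the arm difference. The text does not support that. It gives percent change by arm with t and p for three directions (extension 18.9% against 3.0%, right lateral flexion 23.2% against 10.8%, left lateral flexion 20.0% against 7.7%), and the interaction F values allow the derivation above. Tables 2 to 4 are cited but were not available, and may hold more.

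**Conclusion.** The point holds, at modest weight. Five of eight eta-squared values for time exceed what their F and degrees of freedom give. Left lateral flexion is a true contradiction, by a factor of about 3.9. Extension is overstated by about 26%, and the remaining three by 5% to 8%. This assumes that the statistic is partial eta-squared, as the three reproduced values indicate, and that F is rounded to one decimal.

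Two stronger readings should be resisted. One is that the eta-squared is the wrong item in every case. The printed p supports that for extension, provided it is uncorrected; for left lateral flexion the F is the more likely fault, and for the other three the documents do not say. The other is that the trial's significance claims fall with these values. They do not, because no significance conclusion rests on an eta-squared. The mismatch between F and p for left lateral flexion is a further reason to go to the output, but it is not a consequence of the eta-squared.

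Separately, no eta-squared in the visible text describes the arm contrast. Taken as the effect of stretching, the printed values would mislead several-fold, most visibly for NPRS (0.60 for time, 0.04 for the interaction).

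**What to change.** Check all five against the source output. Start with left lateral flexion and correct either its time F and p or its eta-squared; confirm its interaction F at the same time. For the other four print 0.16 (extension), 0.28 (right lateral flexion), 0.19 (left PPT) and 0.57 (NPRS), unless the output shows that the F is the misprint. Label the statistic partial eta-squared throughout.

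In Statistical Analyses, state that the effect size is also computed for the group-by-time interaction, and print it beside each interaction F.

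This needs no new data, only a reading of existing output and some changes of wording. The downside is that the stated effect sizes become less favourable.

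### The F, degrees of freedom and p-values printed for the three group-by-time interactions credited to stretching do not agree, and the percent-change p-values mix one- and two-sided tests

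*Combined protocol and SAP*

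**What the plan says.** Statistical Analyses names a mixed factorial ANOVA of each outcome by group over time, an independent t-test and a Mann-Whitney test for percent change from baseline to 4 weeks, and a significance threshold of 0.05. It states neither sidedness nor any sphericity correction.

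Results, Changes in ROM, reports the three interactions as follows:

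- Extension: "and a significant group by time interaction ($F_{2,72}=3.6$, $p=0.02"
- Right lateral flexion: "and a significant group by time interaction ($F_{2,72}=2.9$, $p=0.04"
- Left lateral flexion: "and a significant group by time interaction ($F_{2,72}=3.0$, $p=0.03"

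For percent change it reports extension 18.9% against 3.0% (t=2.4, p=0.02), right lateral flexion 23.2% against 10.8% (t=1.8, p=0.04) and left lateral flexion 20.0% against 7.7% (t=2.1, p=0.02). The left lateral flexion time effect is printed as F=3.0, p=0.03, with an eta-squared of 0.30.

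Under Change in NDI, an interaction with almost the same F on the same degrees of freedom is read the other way: "there was no significant group by time interaction ($F_{2,72}=2.8$, $p=0.07".

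**The concern.** The NDI sentence gives the problem away without any software. On the same degrees of freedom, F=2.8 is printed with p=0.07 and F=2.9 with p=0.04. A step of 0.1 in F cannot move p that far, so at least one printed number is wrong.

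The affected sentences carry the trial's positive finding. In the supplied text (Tables 2 to 4 are not available), pain, disability, global change, pressure pain threshold and the other three neck movements show no between-group difference. Which of the three benefits survive depends on which printed number is the error.

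**Working it through.** **Inputs.** 38 participants analysed, 18 and 20 per group (Procedures; Results). Between-subject error df = 18 + 20 − 2 = 36. Three visits give 2 and 2 × 36 = 72; four visits give 3 and 3 × 36 = 108. F, t and p are as printed.

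**Check of the method on other printed results.** With 2 numerator df the upper tail has a closed form, p = (1 + 2F/72)^(−36) = (1 + F/36)^(−36). The NDI interaction, F=2.8, gives 0.067 (printed 0.07). NPRS, F=1.5, gives 0.230 (printed 0.23). Right pressure pain threshold, F=0.98, gives 0.380 (printed 0.38). All three reproduce.

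**The three ROM interactions.** The 5% critical value of F(2,72) is 3.12.

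| Movement | F | Printed p | p at (2,72), range over rounding of F | p at (3,108) |
|---|---|---|---|---|
| Extension | 3.6 | 0.02 | 0.032 (0.031–0.034) | 0.016 |
| Right lateral flexion | 2.9 | 0.04 | 0.061 (0.059–0.064) | 0.038 |
| Left lateral flexion | 3.0 | 0.03 | 0.056 (0.054–0.059) | 0.034 |

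Halving the (2,72) values gives 0.016, 0.031 and 0.028, which misses the printed 0.04.

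**Sphericity.** The correction multiplies both df by epsilon, which is not reported. From epsilon 1 down to the three-visit minimum of 0.5, p rises from 0.032 to 0.066 (extension, passing 0.05 below about 0.70), from 0.061 to 0.097 (right) and from 0.056 to 0.092 (left). At (3,108), p passes 0.05 below epsilon of about 0.46, 0.81 and 0.74 respectively.

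**Is the df label the misprint?** The (3,108) column rounds to all three printed p-values, and Data collection lists a fourth visit at week 8. The df labels are also unreliable elsewhere. The two-group tests of pressure pain threshold are printed as "the change over time was not significantly different between the two groups ($F_{2,72}=0.02$, $p=0.90" (right) and "the change over time was not significantly different between the two groups ($F_{2,72}=0.02$, $p=0.86" (left). At (2,72), F=0.02 would give p=0.98. The NPRS section prints the expected df for such a test: "the improvement did not differ significantly by study group ($F_{1,36}=1.4$, $p=0.24". At (1,36), F=0.02 gives 0.88–0.90 over rounding, which fits 0.90 and comes near 0.86 without matching it.

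Against this, the extension time effect, "during extension over time ($F_{2,72}=6.8$, $p=0.002", fits (2,72), where p=0.0020. At (3,108) it would be 0.0003. If one univariate model with one epsilon produced both extension results:

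- With three visits, the time p needs epsilon 0.93–1.00, and no epsilon gives the interaction p.
- With four visits, the time p needs epsilon 0.62–0.72 and the interaction p needs 0.76–1.00, so the ranges do not overlap.

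Changing the df alone therefore does not repair the extension sentence.

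**Percent change, t on 36 df (equal variances assumed).**

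| Movement | t | Printed p | Two-sided | One-sided |
|---|---|---|---|---|
| Extension | 2.4 | 0.02 | 0.022 (0.019–0.024) | 0.011 (0.010–0.012) |
| Right lateral flexion | 1.8 | 0.04 | 0.080 (0.073–0.089) | 0.040 (0.036–0.044) |
| Left lateral flexion | 2.1 | 0.02 | 0.043 (0.038–0.048) | 0.021 (0.019–0.024) |

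Extension fits only a two-sided test; the other two fit only a one-sided test.

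**Left lateral flexion time effect.** Partial eta-squared = F × df1 / (F × df1 + df2) = F/(F + 36) under either df. For F=3.0 this is 3/39 = 0.077, against a printed 0.30. Values of 0.25 to 0.35 need F of about 12 to 19. The other two ROM values differ less: extension 6.8/42.8 = 0.159 (printed 0.20) and right lateral flexion 13.8/49.8 = 0.277 (printed 0.30). The repeated F and p suggest that the interaction figures were copied into the time effect.

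**The case against.** The arithmetic at (2,72) is hard to dispute. The fair objections concern its reading.

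- **The four-visit reading is a conjecture.** Statistical Analyses gives the 4-week follow-up its own paired t-test, Results reports that follow-up separately with Table 4, and every post hoc comparison uses only baseline, one week and 4 weeks. That describes a three-visit ANOVA. This stands, and it makes the match to (3,108) harder to accept as the explanation. It does not make the printed numbers agree.
- **The errors may be general carelessness, not confined to favourable results.** The left pressure pain threshold interaction (F=0.48, p=0.59) also fails at (2,72), where p is 0.62; an epsilon of about 0.85 would give 0.59. So an unstated correction is possible for that outcome. It cannot rescue the ROM interactions, because correction raises their p-values.
- **A percent-change p-value may come from the Mann-Whitney test.** This is possible and could explain the mixed sidedness. Each p nevertheless stands beside a t with no such label. An unequal-variance t-test makes all three one-sided only at 17 to 18 df, near its minimum, with t=2.4 at its lower rounding edge.
- **Some of the benefit survives.** Uncorrected, the extension interaction is below 0.05 under either df, and two-sided percent change stays below 0.05 for extension and left lateral flexion. This is correct and limits the conclusion.
- **The pressure pain threshold labels and the left lateral flexion time effect are secondary.** Agreed: they show unreliable transcription but are not the between-group benefit.

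**Conclusion.** The concern holds. For all three interactions, the printed F, df and p cannot all be right. If F and df stand, right and left lateral flexion miss 0.05, and extension stays below it only if epsilon exceeds about 0.70. If F and p stand with (3,108) and no correction, all three stay below 0.05, but the test then includes a visit that the printed df do not show. The supplied text cannot settle which is true, so this is not evidence that the interactions are null.

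The percent-change p-values do not share one sidedness on 36 df. With consistent two-sided t-tests, only right lateral flexion changes, to p=0.080. The left lateral flexion time effect is wrong as printed: F and eta-squared contradict each other, taking eta-squared as partial.

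The assumptions are 38 complete cases in each model, equal variances for the t-tests and an unreported epsilon. Because these sentences carry the only reported between-group benefits, they must be corrected before anyone relies on them.

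**What to change.** - Check F, df and p for every ROM effect, and the df of the two-group pressure pain threshold tests, against the SPSS output, and print values that agree.
- State which visits entered each ANOVA and whether a sphericity correction was applied. If a four-visit model was used, correct the df.
- Report all percent-change comparisons with one stated sidedness, two-sided unless one-sided testing was prespecified, and label any Mann-Whitney p-value.
- Correct the left lateral flexion time effect and its eta-squared.
- If the printed F and df stand, report both lateral flexion interactions as non-significant. If t=1.8 stands and tests are two-sided, report the right lateral flexion percent change as non-significant (p=0.08).

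The cost is a check of existing output and text corrections, with no new data. The reported results may become less favourable to stretching.
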